3.1.2 Dose Escalation

Dose escalation will proceed in cohorts of 3 to 6 patients. Patients will not begin treatment at the next higher dose level until all patients treated at the previous dose level have completed the DLT evaluation window and an assessment of DLT has been completed.

Patients will receive s.c. rhIL-15 for the initial period Monday-Friday week 1 and 2. They will be assigned to a dose level sequentially based on their order of entry into the study. The starting dose will be 0.5 mcg/kg/dose and in the absence of dose-limiting toxicities dose escalation will proceed to evaluate dose levels of 1.0 and 2.0 mcg/kg/dose. This initial part of the treatment will be 14 days in length and will be followed by 4 weeks (13 treatments) of alemtuzumab. Only toxicities occurring in this 6-week period will be considered in determining dose escalation. Dose-limiting toxicities are defined in Section 3.1.1. Dose-escalation rules are indicated in the table in Section 3.1.2. As just noted, the first 6 weeks of rhIL-15 and alemtuzumab treatment will be considered in defining criteria for dose escalation and the maximum tolerated dose (MTD).

Dose escalation will proceed in cohorts of 3–6 patients. The MTD is the dose level at which no more than 1 of up to 6 patients experience DLT during the first 6 weeks of treatment, and the dose below that at which at least 2 (of \leq 6) patients have DLT as a result of the drug. If a patient did not experience DLT and did not finish treatment, he or she will not be evaluable for toxicity and will be replaced in the dose level. An additional 3 patients may be enrolled to compensate for inevaluable patients.

Dose escalation table:

Dose Escalation Schedule				
Dose Level	Dose of IND Agent*			

Version Date: 09/24/2021

Dose Escalation Schedule			
Level 1 0.5 mcg/kg/dose			
Level 2 1 mcg/kg/dose			
Level 3 2 mcg/kg/dose			
* Doses are stated as exact dose in units (e.g., mg/m², mcg/kg, etc.) rather than as a percentage.			

Dose-escalation rules:

Number of Patients with DLT at a Given Dose Level	Escalation Decision Rule			
0 out of 3	Enter up to 3 patients at the next dose level			
≥ 2	Dose escalation will be stopped. This dose level will be declared the maximally administered dose (highest dose administered). Up to three (3) additional patients will be entered at the next lowest dose level if only 3 patients were treated previously at that dose.			
1 out of 3	 Enter up to 3 more patients at this dose level. If 0 of these 3 patients experience DLT, proceed to the next dose level. If 1 or more of this group suffer DLT, then dose escalation is stopped, and this dose is declared the maximally administered dose. Up to six (6) additional patients will be entered at the next lowest dose level if only 3 patients were treated previously at that dose. 			
≤1 out of 6 at highest dose level below the maximally administered dose	This is the MTD and is generally the recommended phase 2 dose. At least 9 patients will be entered at the recommended phase 2 dose.			

3.1.2.1 Stopping Rules

Acute ATL patients can have rapidly progressive disease or can have severe disease related metabolic or organ dysfunction that can be exacerbated by treatment with alemtuzumab and fatal events during salvage treatment do occur. If 2 out of the first 15 patients treated in this trial have fatal (grade 5) SAEs regardless of presumed relationship to rhIL-15, entry and all treatment in this protocol will be halted and the data reviewed to better understand the possible contribution of rhIL-15 to these events.

If a patient develops grade ≥3 venous thromboembolism (VTE) during or within four weeks of treatment and while on appropriate VTE prophylaxis, no additional patients will be accrued on the study. Patients already enrolled on the study who are still undergoing treatment will be notified of the event before their next planned alemtuzumab dose and will not receive further doses of alemtuzumab.

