- Diagnosis of adult T-cell leukemia (HTLV-1 associated, chronic or acute), peripheral T-cell lymphoma (angioimmunoblastic, hepatosplenic, or not otherwise specified), cutaneous T-cell lymphoma (Stage III or IV, with leukemic involvement or erythrodermia), or T-cell prolymphocytic leukemia (T-PLL)
- Measurable or evaluable disease
- Adequate organ and bone marrow function as defined in the protocol.

Design:

- This is a single institution nonrandomized Phase I dose escalation study evaluating increasing doses of SC rhIL-15 in combination with alemtuzumab using a standard 3 + 3 dose escalation.
- Treatment will include s.c. rhIL015 daily (M-F) weeks 1 and 2 (dose levels 0.5-2mcg/kg/dose), followed by IV alemtuzumab beginning in week 3 (escalating doses followed by standard dosing in weeks 4-6).
 - Up to 30 patients will be enrolled in this study.

Abbreviated Title: SC IL-15 + alemtuzumab in ATL **Version Date:** 09/24/2021

SCHEMA

Cohort	rhIL-15	Treatment			We	eks		
number Dose		1 reatment	1	2	3	4	5	6
Cohort 1	Calcart 1 0 5 mag/lag/daga			—				
Cohort 1 0.5mcg/kg/o	0.5mcg/kg/dose	alemtuzumab			$\downarrow\downarrow\downarrow$			
Calcout 2	0.1.42.1./1./1							
Cohort 2 1 mcg/kg/dose	alemtuzumab			$\downarrow\downarrow\downarrow$				
Cohort 3	2 mcg/kg/dose	rhIL-15	—					
		alemtuzumab			$\downarrow\downarrow\downarrow$			

TABLE OF CONTENTS

PRÉC	IS	2
SCHE	EMA	3
TABI	LE OF CONTENTS	
STAT	TEMENT OF COMPLIANCE	7
1 I	NTRODUCTION	
1.1	Study Objectives	
1.2	Background and Rationale	
2 E	ELIGIBILITY ASSESSMENT AND ENROLLMENT	24
2.1	Eligibility Criteria	24
2.2	Screening Evaluation	26
2.3	Participant Registration and Status Update Procedures	27
2.4	Baseline Evaluation	27
3 5	STUDY IMPLEMENTATION	28
3.1	Study Design	28
3.2	Drug Administration	31
3.3	Dose Modifications	32
3.4	Clinical Monitoring	32
3.5	Study Calendar	36
3.6	Criteria for Removal from Protocol Therapy and Off Study Criteria	41
4 (CONCOMITANT MEDICATIONS/MEASURES	42
4.1	Premedication for alemtuzumab infusions	42
4.2	Premedication for IL-15	42
4.3	Prophylaxis for Virus and/or Pneumocystis	42
4.4		
4.5	Platelets and RBC support	42
4.6	Prohibited Medications	43
5 E	BIOSPECIMEN COLLECTION	43
5.1	Correlative Studies for Research and Special Studies	
5.2		
6 I	DATA COLLECTION AND EVALUATION	
6.1	Data Collection	
6.2	Data Sharing Plans	48

	6.3	Response Criteria	49
	6.4	Toxicity Criteria	55
7	NI	H REPORTING REQUIREMENTS/DATA AND SAFETY MONITORING PLA	N55
	7.1	Definitions	55

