6.3.1 Definitions

Evaluable for toxicity: All patients will be evaluable for toxicity from the time of their first treatment with IL-15.

Evaluable for objective response: Only those patients who have measurable disease present at baseline, have completed the 6 weeks of therapy, and have had their disease re-evaluated will be considered evaluable for response. These patients will have their response classified according to the definitions stated below.

Evaluable Non-Target Disease Response: Patients who have lesions present at baseline that are evaluable but do not meet the definitions of measurable disease, have completed the 6 weeks of therapy, and have had their disease re-evaluated will be considered evaluable for non-target disease. The response assessment is based on the presence, absence, or unequivocal progression of the lesions.

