10 STATISTICAL CONSIDERATIONS

The primary objective of this trial is to determine the safety, toxicity profile, DLT and MTD of rhIL-15 administered at escalating doses s.c. in combination with alemtuzumab. There are three planned dose levels (0.5, 1, and 2 mcg/kg/dose s.c.) and one dosing strategy (weeks 1 and 2 Monday-Friday). In week three all patients will receive alemtuzumab: 3 mg on day 1, 10 mg on day 2, 30 mg on day 3 and 30 mg on Day 5 of the study. The therapy with alemtuzumab will be continued on weeks 4, 5 and 6 on a 3 x weekly schedule at 30 mg for a total of 4 weeks (13 treatments) of alemtuzumab.

The determination of MTD follows the 3+3 design in which 3 to 6 patients will be enrolled in each combination of dose level. In the initial cohort (Cohort 1), at least 3 patients will be enrolled to receive 0.5 mcg/kg/dose of rhIL-15. In Cohort 2, patients will be enrolled to receive 1 mcg/kg/dose of rhIL-15; and in Cohort 3 patients will receive 2 mcg/kg/dose of IL-15.

The MTD will be based on the assessment of DLT during the first 6 weeks of treatment and will be defined as the dose level at which less than one-third of patients (0/3 or 0-1/6 patients) treated at that dose experience a DLT, with the next higher dose level demonstrating a one-third or greater number of patients (≥2/3 or ≥2/6 patients) having DLT. If a patient did not experience DLT and did not finish the 6 weeks of therapy, this patient will not be evaluable for determination of the MTD and will be replaced in the dose level. An additional 3 to 6 patients will be enrolled at the MTD or, if no severe or dose-limiting toxicities are encountered, the maximum administered dose of rhIL-15, so that a total of 9 patients will be treated at this dose to better characterize the clinical activity of rhIL-15 in this patient population. Accordingly, if all dose levels are evaluated (6 patients per dose level with 9 total patients at the MTD or maximum administered dose) a maximum of 21 evaluable patients will be enrolled. Similarly, if all dose levels are evaluated, the minimum number of evaluable patients required will be 15. An additional 9 patients may be enrolled to compensate for inevaluable patients; thus, bringing the maximum accrual ceiling to 30.

It is expected that accrual can be completed in 60 months.

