Using this dose escalation scheme, the probability of escalating to the next dose level, based on the true rate of DLT at the current dose, is given by the following table (each group will be considered independently of the other):

True toxicity at a given dose	10%	20%	30%	40%	50%	60%
Probability of escalating	.91	.71	.49	.31	.17	.08

The secondary objectives are first to evaluate the potential antitumor activity of the combination of rhIL-15 and alemtuzumab assessing the clinical response rate and time to progression, Another secondary objective is to characterize the biological effects of rhIL-15 administered with alemtuzumab by FACS analysis to define the percentages and absolute numbers of circulating lymphocytes (T and NK cells) and the T-cell subsets naïve, central and effector memory subsets (based on expression of CD52, CD56, CD4, CD8, CD45RO, CD45RA, CD28, CD95, CD194, and CCR7) by flow cytometry. Finally, a secondary objective is to define the effect of the combination on the plasma levels of proinflammatory cytokines using Mesoscale analysis.

Version Date: 09/24/2021

The secondary objectives of the study include characterize the biological effects of rhIL-15 administered with alemtuzumab on the percentages and absolute number of circulating lymphocytes (T and NK cells) and the T-cell subsets naïve, central and effector memory subsets (based on expression of CD52, CD56, CD4, CD8, CD45 RO, CD45RA, CD28, CD95, CCR7, and CD62L) by flow cytometry, and plasma levels of proinflammatory cytokines. Summary statistics will be reported for these measures and considered exploratory.

The accrual ceiling of 24 participants was determined to include the sample size needed for statistical analysis of the safety, toxicity and maximum tolerated dose in this Phase I trial. It provides for 3 inevaluable participants as well as for an expanded cohort of 9 participants at the maximum tolerated dose.

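### The death-count halt covers only the first 15 patients treated, while accrual can run to 21 evaluable and 24 or 30 in all, so later patients have no pre-set death limit

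*Combined protocol and SAP*

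**What the plan says.** Section 3.1.2.1 (Stopping Rules) explains that acute ATL can progress fast, that alemtuzumab can worsen organ dysfunction, and that deaths occur in salvage treatment. It then sets one death-count rule: "If 2 out of the first 15 patients treated in this trial have fatal (grade 5) SAEs regardless of presumed relationship to rhIL-15". When it is met, accrual and all treatment stop while the data are reviewed for a possible contribution of rhIL-15. No reason is given for ending the count at 15.

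Section 10 gives the size of the trial. If all levels are evaluated, "the minimum number of evaluable patients required will be 15" and "a maximum of 21 evaluable patients will be enrolled". It continues: "An additional 9 patients may be enrolled to compensate for inevaluable patients", which makes 30. The Design part of the précis agrees: "Up to 30 patients will be enrolled in this study". The last paragraph of Section 10 gives a different figure: "The accrual ceiling of 24 participants".

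The rule counts patients treated, not patients evaluable for the MTD. Section 6.3.1 likewise says: "All patients will be evaluable for toxicity from the time of their first treatment with IL-15". Under Section 3.1.2, patients are "assigned to a dose level sequentially based on their order of entry into the study".

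**The concern.** The reasons given for the rule do not change at patient 16, but the rule ends there. Because levels fill in order of entry, the patients outside it are those at the highest dose reached, in a refilled level below it, or in the expansion to 9 at the recommended dose. Replaced patients also use up the 15. Read literally, a patient who dies before week 6 without a DLT is inevaluable and is replaced (Sections 3.1.2 and 10), so deaths can themselves lengthen the trial beyond 15.

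At stake is consistency. The sponsor decided that 2 deaths in 15, whatever their presumed cause, call for a halt and review. The same or a higher frequency later would be handled case by case, with no automatic halt.

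**Working it through.** **Inputs.** From Section 10: 3 to 6 patients per level, 9 at the final dose, 21 maximum and 15 minimum evaluable, ceiling 30 or 24, and the escalation table. From Section 3.1.2.1: 2 of the first 15. Fatal rate: an assumption, because the documents give none for this combination. The range comes from the alemtuzumab series in Section 1.2.2.3: 27/174 = 15.5% died within 28 days of the last infusion, or (27 − 14)/174 = 7.5% without deaths attributed to progression. Those were other populations on a longer course.

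**1. Reproduce the plan's figures.** P(escalate) = (1−p)³ + 3p(1−p)²(1−p)³ gives 0.906 at p = 10% and 0.709 at 20%; the table has .91 and .71. The totals also agree: 3+3+9 = 15, 6+6+9 = 21, 21+9 = 30, 21+3 = 24.

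**2. Patients outside the rule.**

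| Path | Patients | After the 15th |
|---|---|---|
| 3+3+9 | 15 | 0 |
| 3+6+9 or 6+3+9 | 18 | 3 |
| 6+6+9 | 21 | 6 |
| Ceiling 24 | 24 | 9 |
| Ceiling 30 | 30 | 15 |

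**3. Chance that the gap matters on a given path.** With a uniform fatal rate f and n uncovered patients: P(Bin(15, f) ≤ 1) × P(Bin(n, f) ≥ 2). The first factor is 0.688, 0.549, 0.319 and 0.300 at f = 7.5, 10, 15 and 15.5%. The products are:

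| f | n = 3 | n = 6 | n = 9 | n = 15 |
|---|---|---|---|---|
| 7.5% | 0.011 | 0.047 | 0.098 | 0.215 |
| 10% | 0.015 | 0.063 | 0.124 | 0.248 |
| 15% | 0.019 | 0.071 | 0.128 | 0.217 |
| 15.5% | 0.019 | 0.071 | 0.125 | 0.210 |

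**4. Weight by how often each path occurs.** The chance of reaching 2 mcg/kg is 0.906² = 0.82 at a DLT rate of 10% and 0.709² = 0.50 at 20%. Of the trials that reach it, 0.647 / 0.522 take 3+3 through the lower levels, 0.315 / 0.401 have one level of 6, and 0.038 / 0.077 take 6+6 (DLT 10% / 20%). With no inevaluable patients, a trial stopped earlier cannot exceed 9 + 6 = 15 and has nobody uncovered.

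I simulated the 3+3 rules over all trials (20,000 per scenario, ceiling 30), including refilling of the level below and expansion to 9. DLT rates by level were 10/10/10, 10/15/20 and 20/20/20%. The inevaluable rates 12.5% (3 of 24) and 30% (9 of 30) are the plan's own allowances, not expected rates.

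| Inevaluable | 2 or more uncovered patients | No halt by 15, then 2 or more uncovered deaths (f = 7.5-15.5%) |
|---|---|---|
| none | 0.28-0.36 | 0.005-0.010 |
| 12.5% | 0.41-0.62 | 0.01-0.03 |
| 30% | 0.47-0.79 | 0.03-0.08 |

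**5. Effect of cumulative limits.** Adding 3 of the first 22, a 21-patient trial has P(halt) = P(≥2 of 15) + P(0 of 15)·P(≥3 of 6) + P(1 of 15)·P(≥2 of 6).
- f = 5%: 0.171 + 0.463 × 0.002 + 0.366 × 0.033 = 0.184, against 0.171 now.
- f = 10%: 0.451 + 0.206 × 0.016 + 0.343 × 0.114 = 0.493, against 0.451 now.

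With 4 of 30 added and 30 patients, the exact patient-by-patient recursion gives 0.198 and 0.546.

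**The case against.** The best defence is that this is a deliberate, front-loaded check on a new combination. Fifteen patients is the shortest full trial, that trial is covered completely, and later deaths are not ignored. Death is an SAE criterion (8.1.2), and every SAE must reach the sponsor's safety office within 24 hours (8.3). The VTE stop has no patient-number limit. The 3+3 rules still act on related grade 3-4 DLTs; on 6+6+9, patients 16 to 18 complete the first six at 2 mcg/kg. Weekly team review (7.4.1) and discretionary suspension (13.1) also continue. All of this stands, and it limits the weight of the point. None of these safeguards sets a death count, however, and the DLT definition requires relatedness to rhIL-15 and does not name grade 5.

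Three stronger readings are tempting and are not supported:
- **That surveillance of late deaths turns on attribution**, because the Clinical Director report in 7.3 leaves out progression deaths. Sections 8.1.2 and 8.3 send every death to the sponsor's safety office whatever its cause.
- **That most trials would leave patients uncovered.** Among trials that reach 2 mcg/kg, the share with two or more uncovered is 0.40-0.59 with none inevaluable and 0.97-0.98 at 30%. Those figures drop the trials that stop early; the shares over all trials are the ones tabulated above.
- **That late patients face a higher fatal risk because of dose.** Section 1.2.4.5 reports 2 mcg/kg/day as the recommended dose from the earlier subcutaneous trial, and alemtuzumab dosing is the same in all cohorts.

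**Conclusion.** The gap is real: in the text available for review, no death limit applies from patient 16, and trials longer than the 15-patient minimum are within the plan. It is a modest weakness in a design choice and does not leave late patients without oversight. Its size depends mainly on replacements: about 1% or less with none, and a few per cent, up to 8%, if the full allowance of 9 is used. These figures assume a fatal rate that is the same at every dose and is borrowed from other populations. The conflict between ceilings of 24 and 30 changes how many patients can be uncovered (9 or 15), not the conclusion.

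**What to change.** In Section 3.1.2.1, keep 2 of the first 15 and extend the same attribution-blind halt for review to all treated patients with cumulative limits near the present boundary. For example, 3 of the first 22 (13.6%) and 4 of 30 (13.3%) sit beside 2 of 15 (13.3%); the clinical team should confirm the thresholds. Under these limits, the case of one death in the first 15 and three in the next six would halt at the third death overall.

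Do not add a 30-day window: the present rule has none, and a window would exclude later related deaths that Section 6.1.1 still records. A separate limit at the top dose is not needed, since the documents give no reason to expect more deaths there.

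The cost is one or two sentences and slightly more pauses. The chance of a halt rises by 0.013 (5% fatal rate) or 0.042 (10%) with 21 patients, and by 0.027 or 0.095 with 30. The action remains a halt for review, not termination.

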3.2 DRUG ADMINISTRATION

rhIL-15 will be given as a subcutaneous (s.c.) injection once daily Monday-Friday following premedication with acetaminophen (preferred) and/or ibuprofen (if reaction despite acetaminophen) as follows:

Version Date: 09/24/2021

• 0.5 mcg/kg/dose during weeks 1 and 2 for cohort 1

- 1.0 mcg/kg/dose during weeks 1 and 2 for cohort 2
- 2.0 mcg/kg/dose during weeks 1 and 2 for cohort 3

Patients will receive up to 10 doses of rhIL-15.

NOTE: Refer to **Appendix F** for calculating IL-15 doses. Included in this section is dose calculation for obese patients.

On Day 1 (or before if clinically indicated) of Week 3, patients will be admitted to the NIH Clinical Center inpatient unit for the alemtuzumab infusions. Patients may be discharged from the inpatient unit and treated in the outpatient clinic when their experience with the treatment indicates that the alemtuzumab can be given safely in an outpatient setting. On Day 1 of Week 3, all patients will receive a 3 mg dose of alemtuzumab with premedication (650 mg acetaminophen and 25-50 mg diphenhydramine). If the dose is tolerated without significant toxicity (\leq grade 2 acute, infusion related toxicity and grade 1 or less skin rash) the patient will receive a 10 mg dose on Day 2 of treatment with the same premedication. If this is well tolerated the dose on Day 3 and Day 5 should be 30 mg with the same premedication.

Alemtuzumab will be administered by intravenous (IV) infusion over a minimum of 2 hours and maximum of 12 hours.

NOTE: Refer to Section **14.2.5** Administration procedures: for more detailed instructions about alemtuzumab infusion times.

After patients have completed and tolerated their initiation dosing of alemtuzumab during week 3 of treatment, treatment will be continued on the t.i.w. schedule at 30 mg with premedication as defined above (650 mg acetaminophen and 25-50 mg diphenhydramine) during weeks 4, 5 and 6.

Insertion of percutaneously inserted central catheter (PICC) or other appropriate vascular access device is permitted.

Treatment may be given on inpatient or outpatient basis. Patients may be hospitalized at the NIH Clinical Center Hospital for convenience and/or social reasons. These hospitalizations will not be considered adverse events and therefore will not require expedited reporting to the IRB.

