3.6 CRITERIA FOR REMOVAL FROM PROTOCOL THERAPY AND OFF STUDY CRITERIA

3.6.1 Criteria for removal from protocol therapy

Prior to removal from study, effort must be made to have all subjects complete a safety visit approximately 30 days following the last dose of study therapy. Criteria for removal from protocol therapy:

- Unacceptable adverse event(s), unless it is felt by the Principal Investigator to be in the patient's best interests to remain on study in exceptional circumstances, including:
 - o DLT as defined in Section 3.1.1
 - o Persistent (> 14 days) treatment-related grade 2 (non-DLT) adverse events
 - o Grade 3 or higher alemtuzumab allergic (infusion) reaction
 - o Third occurrence of alemtuzumab related grade 3 infection
 - o Third occurrence of alemtuzumab related grade 4 hematologic toxicity
 - o Any grade auto-immune cytopenia
 - o Grade ≥3 VTE during or within four weeks of protocol treatment while on appropriate VTE prophylaxis
- The detection of anti-IL-15 neutralizing antibody serum titer ≥ 500 ng/mL as described in **Appendix E** prior to subsequent treatment cycles.
- Evidence the patient has developed autoimmunity that involves a vital organ (heart, kidney, brain, eye, thyroid or adrenal gland, colon, lung). Patients who develop new auto-antibodies without clinical evidence of end-organ dysfunction will be seen by the appropriate internal medicine subspecialists to assess their risk for developing an autoimmune syndrome.
- Inability to receive all doses of rhIL-15 treatment during treatment weeks 1 and/or 2 for any reason.
- Positive pregnancy test
- Completion of protocol therapy including a 30-day safety visit
- Disease progression

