4.4 VENOUS THROMBOEMBOLISM (VTE) PROPHYLAXIS

- Patients will be treated with appropriate anticoagulation prophylaxis for VTE, which may include Enoxaparin, Rivaroxaban, heparin or other anticoagulants (see Section 1.2.5 for rationale).
- If a patient develops grade ≥3 VTE during or within four weeks of protocol treatment despite appropriate prophylaxis, study will be stopped and other patients notified per Section 3.1.2.1.

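### The VTE stopping rule (3.1.2.1 and 4.4) does not settle what happens to rhIL-15 in other patients, and its only notice deadline falls after their last rhIL-15 dose

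*Combined protocol and SAP*

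**What the plan says.** The trigger is a single grade ≥3 VTE, during treatment or in the four weeks after it, in a patient on appropriate prophylaxis. Four places in the combined protocol and SAP bear on what follows.

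- Section 3.1.2.1, VTE paragraph: "no additional patients will be accrued on the study". Patients still under treatment "will be notified of the event before their next planned alemtuzumab dose and will not receive further doses of alemtuzumab". These are the only consequences listed.
- Section 3.1.2.1, fatal-event paragraph, just before it: after two grade 5 events in the first 15 patients, "entry and all treatment in this protocol will be halted and the data reviewed".
- Section 4.4, same VTE trigger: "study will be stopped and other patients notified per Section 3.1.2.1".
- Section 3.6.1 lists "Grade ≥3 VTE during or within four weeks of protocol treatment while on appropriate VTE prophylaxis" among the reasons to take a patient off protocol therapy. This deals with the patient who has the VTE, not with the others.

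On the schedule, Section 3.2 states: "Patients will receive up to 10 doses of rhIL-15". They are given Monday to Friday in weeks 1 and 2. The first alemtuzumab infusion is on Day 1 of week 3, and Section 10 counts 13 alemtuzumab treatments over weeks 3–6.

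**The concern.** rhIL-15 is the investigational agent whose dose is being escalated, yet the operative VTE rule neither stops nor continues it. The neighbouring rule for deaths names all treatment. A careful reader may therefore take the narrower VTE wording at face value and conclude that rhIL-15 goes on. Another reader, starting from Section 4.4, may conclude that everything stops. Both would be acting in good faith on current text.

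The notice clause adds to this. It is keyed to the next planned alemtuzumab dose, which for a patient in weeks 1–2 lies beyond the whole rhIL-15 course. At stake is exposure to the investigational cytokine after the trial's own safety stop has been triggered. That exposure could occur before notice is due, and with the antibody that rhIL-15 is meant to potentiate already withdrawn.

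**Working it through.** **1. The plan's own dose counts.** Take Day 1 as the Monday of week 1.

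- rhIL-15: Days 1–5 and 8–12, so 5 + 5 = 10 doses. This matches Section 3.2.
- Alemtuzumab: Days 15, 16, 17 and 19 in week 3, then three doses a week in weeks 4–6. That is 4 + 3 × 3 = 13 doses, which matches Sections 3.1 and 10.

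**2. The gap under the literal text of 3.1.2.1.** Suppose the VTE becomes known after another patient has had the rhIL-15 dose of day d. The doses left are the rhIL-15 days later than d. The time to the notice deadline is 15 − d days.

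| Day d | rhIL-15 doses left | Days to first planned alemtuzumab |
|---|---|---|
| 1 | 9 | 14 |
| 3 | 7 | 12 |
| 5 | 5 | 10 |
| 8 | 4 | 7 |
| 10 | 2 | 5 |
| 12 | 0 | 3 |

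In every row, 0 of the 13 alemtuzumab doses follow. The last rhIL-15 dose (Day 12) precedes the notice deadline (Day 15) by 3 days. A count of 10 remaining doses arises only if the event is known before the Day 1 dose and the patient nevertheless counts as under treatment. If 4.4 is read as ending all treatment, the middle column is 0 throughout.

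**3. The texts side by side.**

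| | Accrual | Alemtuzumab | rhIL-15 | Notice |
|---|---|---|---|---|
| 3.1.2.1, VTE | closed | stopped | silent | before next planned alemtuzumab dose |
| 4.4, VTE | study stopped | not named | not named | as in 3.1.2.1 |
| 3.1.2.1, deaths | halted | halted | halted | not stated |

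**4. Can it arise?** Section 3.1.2 says "Dose escalation will proceed in cohorts of 3 to 6 patients". It holds back the next dose level until the current one has completed the DLT window, but nothing in it staggers patients within a level. The VTE window also runs four weeks past treatment, while the next level may open once the 6-week DLT window is complete and assessed. A VTE in weeks 7–10 of an earlier patient can therefore coincide with new patients' rhIL-15 weeks. How often is not calculable: no overlap is given, and Section 10 expects accrual over 60 months.

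**5. MTD consequence.** Under Section 10, a patient who has no DLT and does not finish the 6 weeks is not evaluable for the MTD and is to be replaced. A patient in weeks 1–2 at the time of the VTE cannot finish, because alemtuzumab is withdrawn, and replacement is blocked while accrual is closed. This loss occurs whether or not rhIL-15 continues. The two readings differ only in up to 9 further doses of exposure.

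**The case against.** The strongest reply is that there is no real conflict. Section 4.4 sits among the concomitant measures and points to 3.1.2.1 as the operative rule. Its mention of a stop may simply be shorthand for the actions listed there. It does not name rhIL-15 and gives no timing. That stands as a possible reading. It narrows the conflict, but the silence on rhIL-15 and the late notice deadline remain.

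Several stronger readings are tempting, and the documents do not carry them.

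- *A reader might infer that the two sections give opposite orders for rhIL-15.* Neither section gives any order for rhIL-15 by name, so the scope is inconsistent or undefined rather than contradictory in terms.
- *A reader might infer that patients must be kept uninformed until Day 15.* The clause sets a latest time and allows earlier notice. Section 13.1 requires prompt notice to participants on suspension or termination, and the research team meets weekly during treatment (7.4.1). However, 3.1.2.1 does not call this event a suspension or termination, so whether 13.1 applies is unclear.
- *A reader might infer a fixed number of patients at risk from the cohort size.* The cohort size sets no limit on how many are in weeks 1–2 at once.
- *A reader might infer that the continued exposure can add nothing to the MTD decision.* A DLT during rhIL-15 would still count, and Section 6.3.1 makes every patient evaluable for toxicity from the first IL-15 treatment.

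Section 4.4 cites Section 1.2.5 for the rationale of VTE prophylaxis. That section was not in the text available for this check. It may explain why the rule is directed at alemtuzumab, and its absence here is not a fault of the plan.

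**Conclusion.** The point holds as a defect in a stated safety rule. After a grade ≥3 VTE on prophylaxis, the protocol does not say consistently whether other patients go on with rhIL-15. For those in weeks 1–2, the one notice deadline in 3.1.2.1 comes after the drug in question has been completed.

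The size per patient is up to 9 further rhIL-15 doses and up to 14 days before notice is required, for a patient already dosed on Day 1. It falls to 0 doses and 3 days for one dosed on Day 12. These figures assume that staff follow 3.1.2.1 literally, that the schedule runs without delays, and that no earlier notice is given. The number of patients is unknown and may be small.

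For the primary objective, such a patient without DLT is lost to the MTD assessment and cannot be replaced unless accrual reopens.

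**What to change.** Reconcile Sections 3.1.2.1 and 4.4 into one rule, worded the same way in both places, that says explicitly what applies to patients still in the rhIL-15 phase. Tie notification to the next planned dose of either study drug rather than of alemtuzumab alone. State whether the event counts as a suspension or termination under Section 13.1, so that the duty of prompt notice is clear. Which treatments stop is for the sponsor and investigator to decide; nothing here favours one answer.

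The cost is a short amendment to the two sections and earlier contact with the few patients under treatment at the time. Dose levels, sample size and the escalation rule do not change.
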